19.4. Investigator Reporting Requirements

The communication requirements for reporting to BSC are as shown in Table 19.4-1.

Event Classification	Communication Method	Communication Timeline (premarket studies) (MEDDEV 2.7/3: CLINICAL INVESTIGATIONS: SERIOUS ADVERSE EVENT REPORTING UNDER DIRECTIVES 90/385/EEC AND 93/42/EEC)
Unanticipated Adverse Device Effect / Unanticipated Serious Adverse Device Effect	Complete AE eCRF page with all available new and updated information.	Within 1 business day of first becoming aware of the event.Terminating at the end of the study
(UADE/USADE)	Provide all relevant source documentation (de-identified/ pseudonymized) for reported event.	• At request of Sponsor.
Serious Adverse Event (SAE)	Complete AE eCRF page with all available new and updated information.	 Within 3 calendar days of first becoming aware of the event or as per local/regional regulations. Reporting required through the end of the
	Provide all relevant source documentation (de-identified/ pseudonymized) for reported event.	studyAt request of Sponsor
Serious Adverse Device Effects (SADE)	Complete AE eCRF page with all available new and updated information.	 Within 3 calendar days of first becoming aware of the event or as per local/regional regulations. Reporting required through the end of the study
	Provide all relevant source documentation (de-identified/ pseudonymized) for reported event.	When documentation is availableAt Sponsor request.
Device Deficiencies (including but not limited to failures, malfunctions, and product nonconformities) Note: Any Investigational Device	Complete AE eCRF page with all available new and updated information.	 Investigational Device: Within 3 calendar days of first becoming aware of the event. Reporting required through 12 months Control Device: As required per DFU/IFU and as per local/regional regulations

Table 19.4-1: Investigator Reporting Requirements

Event Classification	Communication Method	Communication Timeline (premarket studies) (MEDDEV 2.7/3: CLINICAL INVESTIGATIONS: SERIOUS ADVERSE EVENT REPORTING UNDER DIRECTIVES 90/385/EEC AND 93/42/EEC)
Deficiency that might have led to a serious adverse event if a) suitable action had not been taken or b) intervention had not been made or c) if circumstances had been less fortunate is considered a reportable event.	Provide all relevant source documentation (de-identified/ pseudonymized) for reported event.	Investigational Device: • At request of Sponsor
Adverse Event including Adverse Device Effects (AE/ADE)	Complete AE eCRF page, which contains such information as date of AE, treatment of AE resolution, assessment of seriousness and relationship to the device.	 In a timely manner (e.g., recommend within 10 business days) after becoming aware of the information Reporting required through 12 months
	Provide all relevant source documentation (de- identified/pseudonymized) for reported event.	• At request of Sponsor

Table 19.4-1: Investigator Reporting Requirements

* Please note that pre-market studies are clinical studies with investigational devices or with medical devices that bear the regulatory approval and are not being used for the same approved indications.

19.5. *Device Deficiencies*

Complaint reporting of any device deficiencies for any commercially available products used should be carried out using the manufacturer's processes.

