Assessment	Screening ^a	Baseline	Procedure	Within 1 Day Post- procedure	Prior to Discharge or 7 Days Post- Procedure	30 Days ^b (±7 Days) Office/ Telehealth Visit	6 Months ^b (±30 Days) Office/ Telehealth Visit	1 Year ^b (±30 Days) Office/ Telehealth Visit	2–5 Years ^b [Annual] (±45 Days) Office/ Telehealth Visit	7 and 10 Years ^b (±60 Days) Office/ Telehealth Visit	6, 8, and 9 Years ^b (±60 Days) Telephone
Procedural cine- angiography with post- deployment aortogram ^o	_	_	х	_	_	_	_	_	_	_	_
Balloon aortic valvuloplasty ^p	_	-	X/O	_	_	_	_	_	_	_	—
AE and ADE assessments ^q	_	_	х	х	х	Х	Х	Х	_	_	_
Device deficiencies, SAE, SADE, UADE and CEC event assessments ^r	_	_	х	х	х	х	х	Х	Х	Х	Х
4D CT imaging of prosthetic valve ^s	_	_	_	_	_	Х	_	Х	_	_	_

Table 10.1-1: Data Collection Schedule for ACURATE IDE

Note: X = required; O = optional; - = not required; follow-up should be done by study personnel or as noted below. Visits at 30 days, 6 months, 1–5 years, 7 years and 10 years are office/clinical/in-person or telehealth visits; all required ECG measurements and TTE measurements must be done for all subjects who have a transcatheter valve implanted in the aortic position during the index procedure, even if the associated follow-up assessment is carried out via telehealth.

a: Screening materials for CRC review should be submitted electronically at least 5 days in advance of CRC review.

- b: All follow-up dates will be calculated from the date of the (attempted) index procedure (or from date of randomization for randomized subjects where no implant is attempted). Where indicated, visits must be an office/clinical/in-person visit but may be done in-hospital should the subject be admitted at the time. Subjects who are enrolled but do not receive a study device (test or control) will be followed for 1 year to assess for safety but do not need to have protocol required TTE, ECG or QOL assessments.
- c: Study-specific consent includes screening consent to perform required assessments beyond standard of care that will be evaluated by the CRC to confirm subject eligibility. If the study Informed Consent Form is modified during the course of the study, study subjects will be re-consented as necessary.

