- r: Information on device deficiencies for the test device will be monitored and reported to Boston Scientific. Information on all SAEs, SADEs, UADEs, and CEC events will be monitored and reported to Boston Scientific for enrolled subjects from the time of enrollment through 5 years. After 5 years, serious adverse event assessment (includes SAE, SADE, UADE, and relevant VARC events to be adjudicated by the CEC [see *Note* below]) for test and control device(s) and device deficiencies assessment for test device(s) with associated treatment will be monitored and reported to Boston Scientific for enrolled subjects through termination of the study (or until a subject exits the study). For subjects who are enrolled

Table 10.1-1: Data Collection Schedule for ACURATE IDE

Assessment	Screening ^a	Baseline	Procedure	Within 1 Day Post- procedure	Prior to Discharge or 7 Days Post- Procedure	30 Days ^b (±7 Days) Office/ Telehealth Visit	6 Months ^b (±30 Days) Office/ Telehealth Visit	1 Year ^b (±30 Days) Office/ Telehealth Visit	2–5 Years ^b [Annual] (±45 Days) Office/ Telehealth Visit	7 and 10 Years ^b (±60 Days) Office/ Telehealth Visit	6, 8, and 9 Years ^b (±60 Days) Telephone
------------	------------------------	----------	-----------	---------------------------------------	--	---	---	---	---	--	--

with an attempted procedure but no implanted study valve (test or control), the aforementioned events will be monitored through 1-year post-index procedure. For randomized subjects with no index procedure, the aforementioned events will be monitored through 1-year post randomization. Please refer to Section **19.1** for a list of CEC events and **Table 25.2-1** for definitions of these events, which specify data required for CEC adjudication. Complaint reporting of any device deficiencies for any commercially available products used should be carried out using the manufacturer's processes.

Note: Relevant VARC events after 5 years to be adjudicated by the CEC include the following: mortality, stroke, spontaneous myocardial infarction, acute kidney injury, repeat procedure for valve-related dysfunction, hospitalization for valve-related symptoms or worsening congestive heart failure (NYHA III or IV), new pacemaker, new onset atrial fibrillation or atrial flutter, prosthetic aortic valve malpositioning (valve migration, valve embolization, or ectopic valve deployment), TAV-in-TAV, prosthetic aortic valve thrombosis and endocarditis.

[figure not shown]

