10.10.6. Follow-up (±60 Days) at 6, 8 and 9 Years

All implanted subjects must be evaluated at 6, 8, and 9 years after the index procedure, with a window of ± 60 days. This evaluation may be conducted by telephone. The following assessments must be completed. The ACURATE IDE eCRFs identify the specific data points to be collected.

- Current antiplatelet, anticoagulant (if applicable)
- Serious adverse event (SAE, SADE, UADE, and relevant VARC events to be adjudicated by the CEC) assessment for test and control devices and device deficiencies assessment for test device(s) with associated treatment. Please see Section 10.10.5 for a list of relevant VARC events.

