19.5.1. Boston Scientific Device Deficiencies

All device deficiencies related to the test device or future iterations will be documented and reported to BSC. If possible, the device(s) should be returned to BSC for analysis. Instructions for returning the investigational device(s) will be provided in the study Manual of Operations. If it is not possible to return the device, the investigator should document why the device was not returned and the final disposition of the device. Device deficiencies should also be documented in the subject's source records.

Device deficiencies are not adverse events. However, an adverse event that results from a device deficiency would be recorded as an adverse event on the appropriate eCRF.

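### Table 19.4-1 stops test-device deficiency reporting at 12 months, while other current Protocol sections continue it, so late deficiencies without a serious event may be reported inconsistently

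*Protocol*

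**What the plan says.** Protocol Section 19.4, Table 19.4-1, gives investigators their reporting timelines. For device deficiencies of the investigational device it sets 3 calendar days from awareness and adds "Reporting required through 12 months". The same words stand in the AE/ADE row, where they agree with Section 19.1; the point here concerns the deficiency row only. The SAE and SADE rows of the same table instead say "Reporting required through the end of the study", and the UADE/USADE row also runs to the end of the study.

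Table 10.1-1 (Section 10.1) has a row headed "Device deficiencies, SAE, SADE, UADE and CEC event" assessments, marked as required at every column from the procedure to the 10-year contact. Its note r opens with an undated rule: "Information on device deficiencies for the test device will be monitored and reported to Boston Scientific". For the period after 5 years it is explicit: "deficiencies assessment for test device(s) with associated treatment will be monitored and reported to Boston Scientific for enrolled subjects through termination of the study". The duty ends earlier for a subject who leaves follow-up.

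Sections 10.10.4 (years 2 to 5), 10.10.5 (years 7 and 10) and 10.10.6 (years 6, 8 and 9) each list, among the assessments that must be completed, a "device deficiencies assessment for test device(s) with associated treatment".

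Section 19.1 lists all investigational device deficiencies as reportable with no time limit, and the AE/ADE item in the same list carries a 12-month limit. Section 19.5.1 states, again without a period: "All device deficiencies related to the test device or future iterations will be documented and reported to BSC". Section 16.2 makes the principal investigator responsible for reporting observed deficiencies, and those that could have led to a SADE, also without a period.

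**The concern.** Section 19.1 refers investigators to Table 19.4-1 for the reporting requirements. A site that follows the table as written could carry out the year-4 assessment, find a deficiency, and conclude that it no longer has to be reported. A site that follows note r or Section 19.5.1 would report it.

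The deficiency row itself says that a deficiency which might have led to a serious event, had circumstances been less fortunate, counts as reportable. The row therefore calls near-misses reportable and ends their reporting after the first year. The definition of a device deficiency in Table 19.2-1 includes durability, and Section 5.1.1 describes the valve as a permanent implant. Deficiencies first seen after year 1 are thus within what the follow-up is meant to observe. At stake is uniform capture of late, non-serious deficiency reports for an investigational valve.

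**Working it through.** No sample size, error rate or event rate is involved, so the check sets the passages side by side by period.

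| Period after index procedure | Table 19.4-1, deficiency row | Table 10.1-1, note r and visit sections | Sections 16.2, 19.1, 19.5.1 |
|---|---|---|---|
| To 12 months | Report | Assessment required; report | Report, no time limit |
| After 12 months to 5 years | Reporting ended | Assessment required (Table 10.1-1 row, 10.10.4); note r's opening rule has no date limit | Report, no time limit |
| After 5 years | Reporting ended | Assessment required (10.10.5, 10.10.6); note r says report to study termination or subject exit | Report, no time limit |

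1. **Where they agree.** All passages agree to 12 months. They also agree for enrolled subjects who never receive a study valve, because note r ends their monitoring at 1 year.
2. **Where they conflict.** After 5 years the conflict is explicit: the table ends reporting and note r requires it. Between 12 months and 5 years, the table's limit stands against a required assessment and undated reporting duties.
3. **Contacts affected.** The scheduled contacts after the 1-year visit are years 2, 3, 4, 5, 6, 7, 8, 9 and 10, which is 9. All 9 lie outside the 12-month window. In calendar terms this is 10 − 1 = 9 of the 10 planned follow-up years per implanted subject.
4. **Subjects in scope.** Planned test-device subjects are 750 in the Main Randomized Cohort, up to 170 Roll-In, 50 in the XL Nested Registry, up to 1,000 in Continued Access, and about 50 in the Extended Durability Study (Protocol 7.1; SAP 3.1.2 and 3.3.3). The sum is 750 + 170 + 50 + 1,000 + 50 = 2,020. This is a planned ceiling on subjects to whom the conflicting instruction could apply. It is not a count of lost reports.
5. **What is still caught after 12 months.** Under the same table, UADE/USADE, SAE and SADE reporting runs to the end of the study. A late deficiency that causes one of these reaches the sponsor by that route.
6. **What is exposed.** This leaves deficiencies after 12 months without a serious event. Within the table they have no other route: the AE/ADE row also closes at 12 months, and Section 19.5.1 says that deficiencies are not themselves adverse events.
7. **Analyses.** SAP 5.7.5 plans a summary of site-reported AE/SAE/UADE. The SAP specifies no device-deficiency analysis, and the primary endpoint does not use these reports.

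**The case against.** The strongest case on the other side has four parts.

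- **Only one passage states a longer end point.** That is note r, and only for the period after 5 years. Sections 10.10.4 to 10.10.6 require an assessment and give no reporting end date; Sections 16.2, 19.1 and 19.5.1 give no period at all. This stands. It would be wrong to say that all these sections run to the end of the study. They are, however, consistent with note r and not with a 12-month stop.
- **Near-misses have another duty.** Section 16.2 tells the principal investigator to report deficiencies that could have led to a SADE. This stands in part. The duty is tied to what the protocol requires, so a reader can be led back to Table 19.4-1.
- **Important late valve problems are captured anyway.** Serious events are reportable to study end. CEC adjudication after 5 years includes repeat procedures for valve dysfunction, malpositioning, thrombosis and endocarditis. Core-laboratory echocardiography continues at years 2 to 5, 7 and 10. This stands, and it narrows the consequence considerably.
- **The table may govern only the 3-day clock.** On this reading, later deficiencies would be collected at visits without the expedited timeline. The cell does not say so. It limits reporting itself, in the same form that the SAE and SADE rows use for their end point.

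A reader might infer that late valve failures would go unreported, or that the durability or primary results are compromised. The documents support neither, for the reasons in the third part and because no planned analysis uses deficiency reports.

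**Conclusion.** The inconsistency is real, in current text, and inside one document. The Table 19.4-1 deficiency row cannot be followed as written together with Table 10.1-1 and its note r. Its effect is confined to test-device deficiencies arising after 12 months without a serious event, including those that might have led to one. For these, reporting could differ between sites. Loss is possible, not certain, because a site that works from the visit schedule would still pick them up. The documents give no late-deficiency rate, so the number of reports at risk cannot be estimated; the nine contacts describe the reach of the conflict and not its yield.

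The conclusion assumes that sites may treat Table 19.4-1 as their reporting rule. Section 19.1 invites this, but nothing in the protocol makes the table override the visit schedule. The passages favour the longer period, but a count of passages does not establish the sponsor's intent. The correction is worth making for the safety record and changes no efficacy conclusion.

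**What to change.** Reconcile the Device Deficiencies row of Table 19.4-1 with Table 10.1-1 and note r, Sections 10.10.4 to 10.10.6, and Sections 16.2, 19.1 and 19.5.1. The sponsor should confirm the intended reporting period and state it in the row. The only explicit longer end point is the one in note r, study termination or subject exit, and the other passages are compatible with it. It would help to give the same end point in note r for the stretch between 12 months and 5 years, where its deficiency rule has no date. Leave the 12-month limit in the AE/ADE row, where it matches Section 19.1.

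The cost is one table cell, and optionally one clause in note r, at the next amendment, plus a memo to sites. No new data collection is needed, because the visit schedule already includes the assessment at every contact.

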19.5.1. Boston Scientific Device Deficiencies

All device deficiencies related to the test device or future iterations will be documented and reported to BSC. If possible, the device(s) should be returned to BSC for analysis. Instructions for returning the investigational device(s) will be provided in the study Manual of Operations. If it is not possible to return the device, the investigator should document why the device was not returned and the final disposition of the device. Device deficiencies should also be documented in the subject's source records.

Device deficiencies are not adverse events. However, an adverse event that results from a device deficiency would be recorded as an adverse event on the appropriate eCRF.

19.5.2. Control Device Deficiencies

Device deficiencies related to use of the control device should be reported per the DFU/IFU and per applicable local/regional requirements. If an AE results from a device deficiency or other device issue, the AE must be reported on the appropriate eCRF.

19.6. Reporting to Regulatory Authorities / IRBs / REBs / HRECs / IECs / Investigators

Boston Scientific Corporation will notify all participating study centers if UADEs, SAEs, SADEs, or investigational device deficiencies occur which imply a possible increase in the anticipated risk of the procedure or use of the device or if the occurrence of certain SAEs/SADEs requires changes to the protocol or the conduct of the study in order to further minimize the unanticipated risks.

Boston Scientific Corporation is responsible for reporting adverse event information to all participating Principal Investigators, IRBs/REBs/HRECs/IECs, and regulatory authorities, as applicable.

The Principal Investigator is responsible for informing the IRB/REB/HREC/IEC and regulatory authorities of UADEs and SAEs as required by local/regional regulations.

20. Informed Consent

Subject participation in this clinical study is voluntary. Informed Consent is required from each subject or his/her legally authorized representative. The Investigator is responsible for ensuring that Informed Consent is obtained prior to the use of any investigational devices, study-required procedures and/or testing, or data collection.

The obtaining and documentation of Informed Consent must be in accordance with the principles of the Declaration of Helsinki, the relevant parts of ISO 14155 and the ICH guidelines for GCP, any applicable national regulations, and local Ethics Committee and/or Regulatory authority, as applicable. The ICF must be accepted by BSC or its delegate (e.g., CRO) and approved by the center's IRB/REB/HREC/IEC, or central IRB, if applicable.

Boston Scientific Corporation will provide a study-specific template of the ICF to investigators participating in this study. The ICF template may be modified to meet the requirements of the investigative center's IRB/REB/HREC/IEC. Any modification requires acceptance from BSC or authorized representative prior to use of the form. The ICF must be in a language understandable to the subject and if needed, BSC will assist the center in obtaining a written consent translation. Translated consent forms must also have IRB/REB/HREC/IEC approval prior to their use. Privacy language shall be included in the body of the form or as a separate form as applicable.

The process of obtaining Informed Consent shall at a minimum include the following steps, as well as any other steps required by applicable laws, rules, regulations and guidelines:

• be conducted by the Principal Investigator or designee authorized to conduct the process,

- include a description of all aspects of the clinical study that are relevant to the subject's decision to participate throughout the clinical study,
- avoid any coercion of or undue influence of subjects to participate,
- not waive or appear to waive subject's legal rights,
- use native language that is non-technical and understandable to the subject or his/her legal representative,
- provide ample time for the subject to consider participation and ask questions, if necessary,
- ensure important new information is provided to new and existing subjects throughout the clinical study.

The ICF shall always be signed and personally dated by the subject or legal representative competent to sign the ICF under the applicable laws, rules, regulations, and guidelines and by the investigator and/or an authorized designee responsible for conducting the informed consent process. If a legal representative signs the ICF, the subject shall be asked to provide informed consent for continued participation as soon as his/her medical condition allows. The original signed ICF will be retained by the center and a copy of the signed and dated document and any other written information must be given to the person signing the form.

Note: Centers may use remote consent as allowed by institutional policy and the center's IRB/REB/HREC/IEC.

Failure to obtain subject consent will be reported by BSC to the applicable regulatory authority according to their requirements (e.g., the United States Food and Drug Administration [FDA] requirement is within 5 working days of learning of such an event). Any violations of the informed consent process must be reported as deviations to the Sponsor and local regulatory authorities (e.g., IRB/REB/HREC/IEC), as appropriate.

If new information becomes available that can significantly affect a subject's future health and medical care, that information shall be provided to the affected subject(s) in written form via a revised ICF or, in some situations, enrolled subjects may be requested to sign and date an addendum to the ICF. In addition to new significant information during the course of a study, other situations may necessitate revision of the ICF, such as if there are amendments to the applicable laws, protocol, a change in Principal Investigator, administrative changes, or following annual review by the IRB/REB/HREC/IEC. The new version of the ICF must be approved by the IRB/REB/HREC/IEC. Acceptance by Boston Scientific Corporation is required if changes to the revised ICF are requested by the center's IRB/REB/HREC/IEC. The IRB/REB/HREC/IEC will determine the subject population to be re-consented.

Study personnel should explain that even if a subject agrees to participate in the study and signs an ICF, the heart team and/or the CRC may determine that the subject is not a suitable candidate for the study and/or TAVR procedure. A confidential Screening/Enrollment Log will be maintained by the center to document select information about candidates who fail to meet the general or "other specific" entry criteria.

21. Committees

